Patients who have indicated their consent to be contacted in the future for other studies will be contacted to see if they would be interested in participating in a structured interview either in-person or via telephone to learn more about decision making for older adults about whether to continue colorectal cancer screening. We may also have primary care physicians (PCP) identify patients who they believe would good candidates to participate in the interviews. The PCP will provide the patient with the information sheet and if the patient is interested, the PCP will provide the research staff contact information for the subject to call to indicate their interest in participating. Subjects will be contacted first by telephone and asked their interest to participate in an interview. If they agree to participate they will be asked whether they prefer to conduct the interview in-person or via telephone and study staff will schedule a mutually convenient time. Consent will be implied by the completion of the interview. A cover letter and an information sheet will be sent by mail or email (if subjects provide verbal consent to use personal email) for those interested in an interview. The project goal is to have approximately 20 eligible subjects complete the interview.

We will conduct 60 interviews with up to 20 patients and physicians to evaluate how they interact with the patient decision aid accessed through Patient Gateway. The interviews will be conducted in-person or remotely using a videoconference approved by MGH Brigham (such as Healthcare Secure Zoom or Enterprise Zoom). Each interview using the videoconference will require a waiting room and secure password for that specific meeting. During the interview, the moderator and research subject (physician or patient) will review all the steps in the process. We will audiotape the interviews and a research coordinator will be present during the interview to take notes on the interaction. The interviews will take place at a location on the MGH campus convenient to the participant or via the approved videoconference platform. The interviews will follow structured guides.

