Patients will be recruited from the database of patients who have received decision aids. For patients who have given consent to be re-contacted, study staff will telephone the patient and invite them to participate in the interview. For patients who were not asked about being recontacted for future studies, we will send the patient an invitation letter letting them know about the study opportunity and how to opt-out if they do not want to be contacted. We will also include the study information sheet with the mailing. If the person does not opt-out, study staff will call the patient and ask if she/he is interested in participating. If they agree to participate, study staff will schedule a remote interview using a secure videoconference at a mutually convenient time. The patient will be asked to consent to participating in a secure videoconference and will be asked permission for the researcher to audiotape the call. Consent will be implied by completion of the interview. A letter indicating the date and time of the interview will be sent by mail or email (if the subjects provide verbal consent to use personal email). We will include English-speaking men and women aged 40-80 years. Patients will be asked if they are enrolled in Patient Gateway. If not, they will not be eligible.

Physicians will be recruited from the database of patients who were prescribed a patient decision aid at MGH in the past. We will recruit physicians across a range of practices and specialties.

Patients who received a specialty referral where their physician provisionally ordered a decision aid will also be contacted for feedback. Their feedback on the referral process will be collected through individual interviews or surveys. A cover letter and information sheet describing the study will be mailed to the patients so that they may choose to participate or not. A reminder phone call will be placed for those who haven't completed the questionnaire within a 2-week timeframe. The patients' demographic information will be collected through an RPDR data collection.

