Only participants who have consented to be contacted will be included to provide feedback over the telephone, via email or via focus groups. Study staff will only reach out to those participants who have provided this consent.

Patients for whom a decision aid was provisionally ordered for a specialty referral will be contacted to provide feedback through questionnaires and individual interviews.

Providers who made a specialty referral for a patient will be emailed a survey to complete online or by paper regarding that specific referral. Also, all eligible Partners Healthcare System primary care physicians, specialists, nurses and other clinic staff involved in a patient’s care may be asked to complete either the questionnaire or participate in an

interview. Study staff will work individually with those interested in the interviews, at the time of a specific project.

Participants in the surgery shared decision making project will be adult patients who had surgery at a Partners Hospital for one of the four identified clinical conditions during the recruitment period who have been confirmed that primarily language is English. Participants will also be limited to those who meet the eligibility criteria laid out in Table 1. Children will be excluded as these conditions and procedures are not relevant for children.

Cancer Screening Project 2020:

Participants in the cancer screening shared decision making project will be adults who received a decision aid at a Partners Hospital for one of the four identified clinical conditions in the last 2 years, and English is their confirmed primary language. Participants will also be limited to those who meet the eligibility criteria laid out in Table 2. Children will be excluded as these conditions and procedures are not relevant for children.

Patients in the interviews will be recruited from the database of those who received a decision aid in the past. Patients must also be on Patient Gateway. Physicians will be recruited from the same database and they will be eligible if they prescribed a patient decision aid in the past.

When people who do not speak English are excluded from participation in the research, provide the scientific rationale for doing so. Individuals who do not speak English should not be denied participation in research simply because it is inconvenient to translate the consent form in different languages and to have an interpreter present.

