Patients who received a decision aid in the past will be sent a letter and information sheet to let them know about an upcoming research project and that if they do not want to be contacted about participating, they can opt-out by phone. Potentially eligible patients will be asked if they are users of Patient Gateway. If so, the patient will be asked about their interest in participating in the interview. If the patient is not on Patient Gateway, he/she will not be eligible. If the patient agrees to participate he/she will be sent an information sheet describing the study and a mutually convenient time will be scheduled for the patient to participate in the interview. Consent will be implied by the completion of the interview.

Physicians who prescribed a patient decision aid in the past will be sent a recruitment email asking if they would like to participate in the 60-minute interview. The information sheet will also be included. The physician will be asked to reply to the email to indicate if he/she is interested. For physicians who respond to the email, a mutually convenient time will be scheduled for the physician to participate in the interview. We will recruit physicians across a range of practices and specialties. All emails that are sent for recruitment will be sent in accordance with Partners' institutional guidelines for information security. Consent will be implied by the completion of the interview.

Patients who received a specialty referral where their physician provisionally ordered a decision aid through the Clinical Referral Management System will also be contacted by the study staff for feedback on the referral process. Their feedback will be collected through

individual interviews or surveys. The information will help us to better understand decisions around the referral process. A cover letter and information sheet describing the study will be mailed to the patients so that they may choose to participate or not. Any information provided by patients will be kept confidential. The patients' demographic information will be collected through an RPDR data collection.

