survey completion. Patients who did not opt-out will receive a secure REDCap survey link by email at 5 time points: one-week post baseline visit, 6 months, 12 month, 18 months and 24 months. The protocol for following up at each time point will be the same: 1) the patients will receive an automated reminder from REDCap one week after each survey is sent if the patient has not responded, 2) one reminder phone call will be made one week after the automated response is sent if the patient has not responded. Study staff will offer to complete the survey over the phone, if the patient would prefer.

Provide details of remuneration, when applicable. Even when subjects may derive medical benefit from participation, it is often the case that extra hospital visits, meals at the hospital, parking fees or other inconveniences will result in additional out-of-pocket expenses related to study participation. Investigators may wish to consider providing reimbursement for such expenses when funding is available

Those patients participating in an individual interview will receive \$20 after completion of the 45-minute interview. Patients completing a 1 hour audiotaped interview will receive \$40. Focus group participants will receive \$60 after completion of the 90 minute session. Participants will not receive any remuneration for completing questionnaires, including the specialty referral interview. Participants who will be participating in a 90-minute individual interview will receive \$40 after completion of the interview. Patients participating in the recontract survey mental health study will not receive compensation.

Participants in the interviews about the patient decision aids prescribed through EPIC and accessed through Patient Gateway will receive \$50 in cash to thank them for their time

Participants who receive the surgery shared decision making survey in the mail will receive \$2 cash as an incentive to promote survey completion.

Cancer Screening Project 2020:

Participants who receive the cancer screening shared decision making survey by mail will receive \$2 as an incentive to promote survey completion.

Clinician's participating in surveys or interviews will not be compensated.

Participants in the *Path to Lifestyle Change* program will not receive any incentives.

For guidance, refer to the following Partners policies:

Recruitment of Research Subjects

<http://healthcare.partners.org/phsirb/recruit.htm>

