record numbers; removing face sheets or other identifiers from completed surveys/questionnaires; proper disposal of printed computer data; limited access to study data; use of password-protected computer databases; training for research staff on the importance of confidentiality of data, and storing research records in a secure location.

NOTE: Additional measures, such as obtaining a Certificate of Confidentiality, should be considered and are strongly encouraged when the research involves the collection of sensitive data, such as sexual, criminal or illegal behaviors.

As the goals of this study are to 1) demonstrate the ability to introduce and disseminate SDM programs to patients, 2) assess and understand “prescribing” utilization, trends and patterns by clinician and across practices, 3) obtain feedback from patients about receiving SDM programs, their decision preferences and comfort with making a decision, and 4) assess the quality of shared decision making for elective surgical decisions.

The study staff will process and manage the distribution and return of programs and questionnaires. Once questionnaires have been returned, the study IDs will be removed so that any ability to link the questionnaires back to patients is removed prior to any review, database entry or analysis of the data. Patient identifiers on the program log (name, address and phone number) will be removed before a copy of it is given to study staff. The study database will not contain any patient information. In this way, the privacy of the subjects and confidentiality of the data collected will be maintained.

No personal information will be captured during the qualitative feedback sessions. Patient privacy will be maintained. All notes will be stripped of any personal identifiers and/or HIPAA related information.

The-interviews will be recorded. The interview data will be identified by a code only. Once the interview is completed, we will not keep the link that ties the participant to the interview. To ensure confidentiality, all study materials will be kept in locked file cabinets and on electronic drives on a Partners password-protected computer to which only the study staff has access.

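### Can 60 Patient Gateway interviews be held with up to 20 patients and physicians?

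*Combined protocol and SAP*

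**What the plan says.** Research Design and Methods gives the only size for this sub-study: "We will conduct 60 interviews with up to 20 patients and physicians". The same paragraph has a moderator go through the process with one research subject, a physician or a patient, so these are not group sessions.

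For patients, the next paragraph of that section says "study staff will schedule a remote interview using a secure videoconference at a mutually convenient time". For physicians, Recruitment Procedures describes an email "asking if they would like to participate in the 60-minute interview", followed by one agreed time. Equitable Selection of Subjects repeats the source of patients ("Patients in the interviews will be recruited from the database of those who received a decision aid in the past") without a number.

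The remuneration text in Recruitment Procedures has two lines that could bear on length. One reads "Participants in the interviews about the patient decision aids prescribed through EPIC and accessed through Patient Gateway will receive" 50 dollars in cash, with no duration. The other reads "Patients completing a 1 hour audiotaped interview will receive" 40 dollars, and is not tied to this sub-study. Clinicians are not paid. Privacy and Confidentiality says of recorded interviews: "Once the interview is completed, we will not keep the link that ties the participant to the interview".

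**The concern.** Read literally, the sentence asks for more interviews than its own cap permits. If each person is interviewed once, 20 people cannot supply 60 interviews, and neither can 40. The cap is itself unclear: "up to 20 patients and physicians to evaluate how they interact with the patient decision aid accessed through Patient Gateway" does not say whether 20 covers both groups together or each separately.

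Because no other section sizes this sub-study, a reader cannot resolve the conflict by looking elsewhere. An ethics committee would want to know how many people will be approached, how long each will be asked to give and, since patients are paid and clinicians are not, how many payments are implied. Had an estimate or a test rested on the count, a threefold discrepancy would be serious.

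**Working it through.** **Inputs.** Stated interviews: 60 (Research Design and Methods). Cap: up to 20, total or per group not specified (same sentence). Interviews per participant: 1, from the singular wording and single agreed time in Research Design and Methods for patients and in Recruitment Procedures for physicians. Physician interview length: 60 minutes (Recruitment Procedures).

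**Formula.** Interviews = participants × interviews per participant.

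**Attempt to reproduce 60.**

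| Reading | Participants | Interviews each | Interviews |
|---|---|---|---|
| 20 is the total | 20 | 1 | 20 |
| 20 per group | 20 + 20 = 40 | 1 | 40 |
| 20 is the total, repeats | 20 | 60/20 = 3 | 60 |
| 20 per group, repeats | 40 | 60/40 = 1.5 | 60 |
| Up to 20 patients, physicians uncapped | 20 + 40 = 60 | 1 | 60 |

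The first two rows follow the design as described and miss 60 by 60 − 20 = 40 and 60 − 40 = 20. The third matches exactly but needs three sessions each, which no section describes. The fourth is not a whole number of sessions per person. The fifth matches only if the cap applies to patients alone and at least 40 physicians take part, and nothing in the text suggests that many.

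**Reading 60 as a length.** If *minute* was dropped, the sentence plans 60-minute interviews with up to 20 patients and physicians. This agrees with the physician invitation in Recruitment Procedures and gives patients the same length. It also fits the scale of a neighbouring exercise: the interviews on whether older adults should continue colorectal cancer screening aim for about 20 completed interviews. Only the total-or-per-group question is left, 20 against 40 people.

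**What uses the figure.** The endpoints are listed in Research Design and Methods: dissemination of the programs, prescribing patterns, patient feedback, and quality of shared decision making for elective surgery. None is defined by a number of interviews. These interviews follow structured guides and yield descriptive feedback, and the documents give no alpha, power, effect size or precision target for them.

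**The case for a change.** The best case for asking for a correction is that the contradiction is plain and unaffected by redaction or extraction, that this is the only size statement for the sub-study, and that one or two sentences would cure it. The protocol form itself asks for the number of subjects, and here the answer can be read as 20 or 40. All of that is true, and the mismatch between count and cap stands.

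Three further arguments do not hold up:

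- **Patient interview length.** It can be said that this stays unstated even after the slip is mended. But restoring the dropped word in the design sentence gives the length for patients and physicians alike. The two remuneration lines then do not matter.
- **The privacy rule.** Discarding the link after an interview prevents sessions from being matched to one person. It does not limit how many sessions are held, and it is written for recorded interviews in general.
- **60 is impossible as a count.** This relies on silence about repeats. Three sessions for each of 20 people gives exactly 60, and an error in the cap is not excluded. One therefore cannot say that 60 is the figure to delete. The total-of-20 reading needs no added word, whereas the per-group reading needs an *each* that is not there, but this does not settle the matter.

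What survives is an unclear sentence whose cure is for the investigators to write down what they already intend.

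**Conclusion.** The count and the cap do not reconcile on a one-interview-each reading: 20 or 40 interviews against a stated 60, an excess of 40 or 20. The most economical explanation is that 60 is the length in minutes and a word was lost. This is an inference from the physician invitation; a mistaken cap or undescribed repeat interviews remain possible.

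No change to the plan follows. Investigators running a small descriptive interview study know how many people they mean to speak to. Completing 20, 40 or 60 interviews would alter the depth of the feedback, but no test, endpoint or conclusion in the documents. Correcting the sentence would improve its wording and gain nothing statistically. The conclusion rests on the interviews staying descriptive, as the documents present them; it would need revisiting only if a quantitative claim were attached to their number.
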